2. PROJECT SUMMARY

2.1. Project Description

The objective of this project is to evaluate the impact of proactive calls by LAs to households at risk of homelessness, with the aim of preventing homelessness through early and targeted intervention. The early intervention is targeted using the results of a predictive model, but the model is not the subject of the evaluation: the sample will be determined by the model, so both intervention and control groups will have been identified as at-risk by the model; what will differ between groups is whether they are telephoned by the LA. The model uses individual-level as well as household data to identify risk factors (and allow for targeted support at individual level), but the risk levels and factors that are produced as an output are at household-level. The analysis of outcomes will also be conducted at household-level: whether the household has become homeless and is owed a relief duty. A 'household' is the subject of a homeless application; it could refer to an individual as well as a family unit (in any configuration).

The trial will consist of an impact evaluation (IE), accompanied by an Implementation and Process Evaluation (IPE) and an economic evaluation. The intervention will be delivered by four LAs, and their use of the predictive model is being funded by MHCLG. Through the Centre for Homelessness Impact (CHI), MHCLG also funds the independent evaluation of the intervention conducted by Verian.

This project is being conducted as a randomised trial, with households as the unit of randomisation and a household-level outcome measure, with data collection at 2 and 9-months after the end of a 1-month implementation period. The primary outcome measure is whether households are owed a relief duty because they have become homeless. This can happen if a homeless application was made by a household member or by someone on their behalf, and (i) the housing authority assessed the application and accepted that the household was homeless and was owed a 'relief

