5.2. Study Design

Study design details

The IE is a two-arm parallel RCT with randomisation at the household level, blocked by LA and predicted risk of homelessness. Households in the 'treatment' arm will receive proactive support (in the form of a phone call) from their LA in addition to BAU support. Households in the 'control' arm will only receive BAU support from LAs. This varies between LAs and refers to the range of activities that LAs and local organisations (including the third sector) undertake, and services they offer, to prevent and reduce homelessness. This support is available to households in both

the intervention and control arms, the difference is whether they receive a phone call that signposts them to the relevant support for them.

Allocation

Verian will randomly allocate households into the trial's two arms with equal probability, with a blocking design to ensure that the sample within each LA is as well balanced as possible on predicted risk of homelessness at the trial's start.

To assign blocks, we will independently sort each LA's sample by a continuous risk score generated by Xantura and then sequentially allocate households to blocks of four, following the sorted order. The target sample size at this point will be a multiple of four, so all blocks should be fully filled. If this is not the case, any remaining households will be entered into the final block. Once sorted into blocks, we will randomly assign households within each block so that every block of four contains two treatment households and two control. If the final block contains an odd number of households, we will randomise those households freely. The sample is thus stratified by LA and then risk score within LA.

We will randomise using the R package 'randomizr' (Coppock, 2019). One researcher will conduct the randomisation, but the code will be checked by another researcher to ensure it has been conducted correctly and can be reproduced. Once conducted, the randomisation code will be saved and made available in the OSF pre-registration that will be published for this trial.

Batching

We will deliver the sample to LAs in three batches, at the start of the first, second, and third months of the trial. We will run the randomisation separately for each batch, using up-to-date risk scores generated by Xantura.

Update to protocol: Study design in Test Valley

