3. We will exclude Test Valley from any of the pre-registered analyses that make use of predicted risk scores or blocks assigned by risk scores, i.e. the Primary and Secondary Analyses.
4. We will use the pre-registered sensitivity analysis that does not include predicted risk score as a covariate to gauge the impact of the intervention in Test Valley. These will be run with and without Test Valley.
5. We will report estimates of impact from that analysis across the participating LAs to provide indicative evidence of how the planned approach using Xantura's predictive risk scores compares to the 'rules-based approach' taken in Test Valley. We must note that this is a strictly exploratory comparison, and it will not account for other differences between the LAs which might plausibly have driven differences in the efficacy of the intervention.

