6.2. Recruitment

Xantura will identify at-risk households using data supplied by participating LAs. They will apply the predictive model shortly before the start of the first, second, and third months of the trial to ensure that risk scores are up-to-date for each batch.

For each batch, Xantura will select a target number of eligible households from each participating LA, favouring those with the highest risk scores. Households will only be eligible for inclusion in one batch, so they cannot be selected if they were part of a previous batch. Xantura will aim to select 168 households from each LA for the first batch, and then 166 for each of the second two batches (totalling 500 across all batches, though see **9.2 Attrition Assumptions** for alternative scenarios). The target of 500 households per LA was set by CHI during its project conception.

[figure not shown]
Because the sample size for each batch is capped, it is likely that some households will meet the eligibility criteria but will not be selected for that batch. When the next batch is drawn, Xantura will re-run the predictive model and any such households who still meet the eligibility criteria will be eligible for selection follow the process set out above.

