9. SAMPLE SIZE AND POWER CALCULATION

9.1. Sample Size / Power Calculation

There is little evidence at present for the likely scale of any treatment effects, or for the distribution of baseline risk scores in each participating LA or how well they really predict future homelessness. Each of these could impact power. Furthermore, the sample size is limited by the number of at-risk households in the population and LAs' capacity to deliver the treatment, of which we expect the latter to be more limiting. We therefore start here from the planned sample size that LAs initially consented to when they agreed to take part (500 per LA) and consider the implications of various scenarios in which the achieved sample is lower than planned due to delivery constraints or attrition (e.g., missing data), under a set of conservative assumptions.

We present below the Minimum Detectable Effect Size (MDES) for effect of treatment on the (binary) primary outcome measure under each scenario. MDES are shown as absolute percentage point differences, provided as ranges because they vary depending on baseline proportions. To minimise the risk that our power calculations overstate power, we make the conservative assumption that the planned baseline covariates do not account for any variance in the primary outcome. This is in practice unlikely to be the case, although they may not greatly improve power if baseline risk scores are high in most sampled households.

Under our assumed likely scenario, our MDES at alpha = 0.05 and power (beta) = 0.8 is a 2-7 absolute percentage point difference in the proportion of households becoming homeless between treatment and control. Ranges are provided because the MDES expressed in absolute terms varies with base probability of homelessness under the null hypothesis (Figure 3).

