9.2. Attrition Assumptions

We conducted power calculations prior to confirmation of the final list of participating councils. When doing this, we considered the following scenarios:

Scenario A (our planned main scenario) – Five LAs take part; 500 households recruited and randomised per LA, with 20% lost as post-randomisation attrition. Achieved n = 2,000.

Scenario B – as Scenario A, but the recruited sample in Batches 2 and 3 are reduced by 20% due to delivery constraints that become apparent in Batch 1. Achieved n = 1,736.

Scenario C – as Scenario A but one of the five LAs withdraws before the start of the trial. Achieved n = 1,600.

RBKC withdrew before the start of the trial (December 2024), so Scenario C will represent the expected main scenario at the time this protocol is first registered.

Scenario D – as Scenario B but one of the five LAs withdraws before the start of the trial. Achieved n = 1,388.

The attrition assumption covers participants opting their data out of the evaluation, gaps in administrative records, or participants moving out of the LA during the trial period. We expect such instances to be few, so the figure of 20% is likely to be conservative. It was arrived at by CHI early in the trial's development and has been maintained in the absence of strong evidence justifying amending it. Note that its impact is minor – adjusting assumed attrition in Scenario A from 20% to 5% changes the range of MDES from 2-7pp to 2-6pp.

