10.6. Sensitivity Analysis

Alternative analysis methods

To test the robustness of the trial's main findings to different analysis methods, we will repeat the primary analysis introducing several variations.

Firstly, we will re-run the primary model using a probit link function instead of a logit, per CHI's Statistical Analysis guidance. This analysis tests whether the trial's results hold under an alternative and equally justifiable approach to that taken in the primary analysis.

Secondly, we will trial an alternative analysis in which the indicators for LA and baseline risk are replaced with a vector of dummy variables representing the blocks to which households were assigned. This analysis would be a conditional logistic regression, which is better suited to handling many small strata that do not gain precision as the study's sample size increases (since the stratum size remains constant at 4 households). This analysis captures the impact of treatment in the event that predicted risk scores vary in predictive power across LAs.

And thirdly, we will repeat the main analysis but dropping all predictor variables apart from treatment. This approach is likely to lose power, but if in practice the baseline risk scores of households recruited into the trial are generally high and with little variation, then the loss may be minimal. We will run this analysis both including and excluding cases from Test Valley.

Compliance analysis (CACE)

To complement the primary ITT analysis, we will also conduct Complier Average Causal Effect (CACE) analysis to provide a more accurate measure of treatment efficacy amongst 'compliers'. We will apply the instrumental variables approach using the Two Stage Least Squares (2SLS) method.

For a household in the treatment arm to be considered 'compliant', the following must be true:

- The LA call handler successfully made telephone contact with an adult member of the household
- They were able to complete the treatment call (i.e., they were not cut off prematurely)
- If any member of the household submitted a homelessness application within the trial period, the call took place before that application was made.

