12.3. Data Collection and Processing

Data Sources

We will collect data on the intervention costs from the LAs through a Cost Data Submission Tool and triangulate these – where relevant and applicable – with appropriate external data sources. The study's impact evaluation will provide estimates of the number of beneficiary households (households whose members avoid being owed a relief duty because they have become homeless) required for the estimation of cost savings resulting from the intervention.

Data Collection Procedures

A Cost Data Submission Tool in the format of an Excel file will be developed by Simetrica-Jacobs. This will be distributed to the LAs participating in the project as part of the IPE's qualitative data collection process (TBC).

The cost estimates obtained from returned submissions forms will be scaled up in line with the project target population in each LA to represent the whole project.

Data Collection Schedule

- Cost data submission form developed – 30th September 2024 (Simetrica-Jacobs)
- Cost data submission form sign-off – 30th October 2024 (CHI/consultation with LAs - TBC)
- Cost data submission form distribution – TBC

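### Test Valley is removed from the primary and secondary analyses, but the sample definition and stated MDES still count it, and the one pooled analysis that keeps it drops LA and covers only the primary outcome

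*Protocol*

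**What the plan says.** Section 5.2 explains that Test Valley could not supply a key predictor, so no risk scores exist there. Its households are instead chosen by debt-based criteria and risk tiers, and are randomised within the LA without risk-score blocks. Item 3 then states "We will exclude Test Valley from any of the pre-registered analyses that make use of predicted risk scores" or the blocks built from them, and names the primary and secondary analyses. Item 4 turns to the sensitivity analysis without the risk score, run with and without Test Valley. Section 10.6 defines that analysis: "we will repeat the main analysis but dropping all predictor variables apart from treatment". Section 10.7 adds exploratory treatment-by-LA interaction and subsample models without the risk score, so that Test Valley can enter.

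Other sections keep the four-LA position. Section 6.1 describes the target group across four LAs. Section 10.1 makes the analytic sample every randomised household with a primary outcome. Section 9.1 says "our MDES at alpha = 0.05 and power (beta) = 0.8 is a 2-7 absolute percentage point difference", and section 9.2 names Scenario C (four LAs, 1,600 analysed) as the expected main scenario. Section 10.6 says that its variations repeat the primary analysis. Section 12.3 says cost returns "will be scaled up in line with the project target population in each LA to represent the whole project" and takes the number of beneficiary households from the impact evaluation.

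**The concern.** A reader of sections 6.1, 9 and 10.1 would expect the primary result to rest on about 1,600 households in four LAs. Section 5.2 makes it about 1,200 in three. If the result is null, it would be read against a detectable difference that the analysis was not sized to detect.

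The supporting analysis is also weaker than it need be. LA is known for every household and randomisation is within LA, so the pooled model can keep LA terms without a risk score. Dropping them costs precision. If base rates differ between LAs, it also makes the odds ratio less comparable with the LA-adjusted primary one. For the prevention duty, Council Tax and discretionary payment outcomes, no pooled estimate that includes Test Valley is specified.

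**Working it through.** **Inputs.** Alpha 0.05 two-sided and power 0.80 (Table 7). Allocation to "two arms with equal probability" (5.2). "The target of 500 households per LA was set by CHI during its project conception" (6.2). Scenario A has "500 households recruited and randomised per LA, with 20% lost as post-randomisation attrition" (9.2), and Scenario C is the same with four LAs. The covariates are assumed to explain no variance (9.1).

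**Sample.** Four LAs: 4 × 500 × 0.8 = 1,600, or 800 per arm. Without Test Valley: 3 × 500 × 0.8 = 1,200, or 600 per arm. Planned share removed: 500/2,000 = 25%.

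**Formula.** With n per arm, base rate p0, p1 = p0 − d and mean p̄:

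power = Φ{[d − 1.96·√(2p̄(1−p̄)/n)] / √([p0(1−p0) + p1(1−p1)]/n)}

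The MDES is the d that gives 0.80.

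**Reproducing Table 7.** At base rates of 3% and 50% the MDES in percentage points is: A 1.80-6.25, B 1.90-6.70, C 1.97-6.98, D 2.08-7.49. Rounded up, these give the printed 2-7, 2-7, 2-7 and 3-8. Scenario A with 5% attrition gives 1.67-5.74, matching the 2-6 in section 9.2. The 3% is inferred from this match, because Figure 3 is not shown.

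**With and without Test Valley.**

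| Analysed (per arm) | MDES, 3% base | MDES, 10% base | MDES, 50% base | Power for 7 points at 50% base |
|---|---|---|---|---|
| 1,600 (800) | 1.97 | 3.82 | 6.98 | 80.2% |
| 1,200 (600) | 2.20 | 4.34 | 8.05 | 68.2% |

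Worked example for the last column, p0 = 0.50, p1 = 0.43, p̄ = 0.465:
- n = 800: (0.07 − 1.96 × 0.02494)/0.02488 = 0.849, so power is 80.2%.
- n = 600: (0.07 − 1.96 × 0.02880)/0.02873 = 0.472, so power is 68.2%.

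At a 50% base rate the MDES grows by 8.05/6.98 = 1.15, as √(1,600/1,200) = 1.155 predicts. With the protocol's rounding up, the three-LA range is 3-9 points.

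**Does adding Test Valley restore the power?** Only if the effect there is similar. Let f be the Test Valley effect as a fraction of the effect elsewhere, with 400 analysed and the same base rate. The pooled difference is d(0.75 + 0.25f). Including Test Valley breaks even when 0.75 + 0.25f = √(1,200/1,600) = 0.866, so f = 0.116/0.25 ≈ 0.46. For d = 6.98 at a 50% base rate, pooled power is 80.0%, 74.7%, 68.8%, 62.3% and 55.5% at f = 1, 0.75, 0.5, 0.25 and 0, against 67.9% without Test Valley.

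**Is a four-LA model valid?** It was simulated under assumed parameters: 400 per LA, with risk set to a constant in Test Valley so that its LA dummy absorbs it. Rejection under no effect was 5.2% with Test Valley and 4.7% without (2,000 runs, Monte Carlo SE √(0.05 × 0.95/2,000) = 0.5 points). At a log odds ratio of −0.3 common to all LAs, power was 81% against 71%, or 79% against 71% with a lower Test Valley base rate (1,000 runs each).

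**The case against.** The strongest reply is that Test Valley differs by more than one missing covariate. It has its own eligibility rule and unblocked randomisation. Section 2.1 does say "the model is not the subject of the evaluation", and a reader might infer that targeting is irrelevant and that all randomised households belong in the primary estimate. The same sentence goes on to say that the model determines the sample and that both arms are identified by it. Read whole, it supports a primary estimate confined to model-selected households. This stands, and so the primary analysis need not be changed to four LAs.

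Three further replies carry weight. Leaving out a whole LA for a reason unrelated to outcomes keeps randomisation intact in the others. Section 10.7 already plans models that include Test Valley and keep LA terms. And because allocation is equal within each LA, omitting LA from the pooled model brings little or no bias. But the 10.7 models look for differences between LAs; they do not give one adjusted four-LA effect, and the secondary outcomes are not named.

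It could also be said that section 9 records calculations made before the participating LAs were confirmed. Yet that section was updated for another LA's withdrawal and not for this exclusion.

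A reader might also infer that the economic evaluation pairs four-LA costs with a three-LA effect. The protocol does not say so. It leaves open which LAs supply the effect, so this is a gap to close and not a demonstrated mismatch.

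**Conclusion.** The point holds as one of consistency and reporting. The primary analysis as specified has about 1,200 households, an MDES of about 2.2 to 8.05 points and about 68% power for 7 points at a 50% base rate. The protocol still presents 1,600 and 2-7 points. The pooled Test Valley-inclusive analysis omits LA without need and stops at the primary outcome.

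The documents do not support the stronger readings that the exclusion biases the result, or that including Test Valley would simply recover the lost power. The gain needs a Test Valley effect of more than about half that elsewhere, and section 5.2 itself warns that differences between LAs may drive efficacy.

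The figures rest on planned numbers (500 per LA, 20% attrition); achieved Test Valley numbers are not given. The 50% base rate comes from a Table 7 footnote about model-identified households and may not apply to those chosen by rules.

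**What to change.** 1. In section 9, restate the MDES for about 1,200 analysed. In 10.1, limit the primary analytic sample to the three model-based LAs, and note in 6.1 that Test Valley was selected by a different route.
2. Beside the three-LA result, report a pooled four-LA intention-to-treat model with treatment and LA dummies, for the primary and all three secondary outcomes. Either omit the risk score, or centre it within LA and set it to 0 in Test Valley. State that the estimate spans two targeting routes, and give the condition under which it gains power. Tier dummies are optional and depend on the spread across tiers.
3. State in section 12 that the economic evaluation uses the same LAs for costs and for effects.

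The cost is wording and one extra model per outcome. Version 3.0 is dated 18 December 2025 and the primary data pulls run from February to April 2026, so the primary-outcome addition can be fixed in advance if made before those data are analysed. Table 5 puts the 2-month secondary pulls in August to October 2025. If those data have already been analysed, label the pooled secondary model as added afterwards.

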5.3. Research Setting

This research will be conducted across four LAs across England:

- London Borough of Barking and Dagenham
- Newham
- Stockport
- Test Valley

These LAs were selected by CHI via a competitive expression of interest process to ensure some generalisability and scalability of results. Applications were open to all unitary LAs in England. Completed applications were independently scored by two internal CHI reviewers against a standardised rubric, moderated by a third reviewer, and approved by CHI's Grants and Evaluation Committee.

CHI also initially engaged Kensington and Chelsea, who were unable to participate in the trial but who will participate in the Implementation and Process Evaluation.

6. TARGET POPULATION

6.1. Eligibility

The target group for this research is the population of households at risk of homelessness within the next 3-6 months, across the four LAs participating in this trial (see **5.3 Research Setting**).

Eligibility criteria

Households will be deemed 'at risk' according to a predictive model run by Xantura. The model generates a household-specific risk score (0-100) indicating the expected likelihood of the household becoming homeless in the next three to six months under BAU conditions. Any household with a score greater than or equal to 50 is considered 'at risk' and is eligible for the trial unless they meet one of the exclusion criteria set out below.

Exclusion criteria

Households who meet any of the following exclusion criteria will not be eligible, regardless of risk score:

- They are already participating in a CHI trial
- They ask not to receive the intervention
- They ask for their data not to be used in this trial
- They are already receiving intensive support from LAs via a Relief or Prevention Duty issued in the last 6 months

- They have already been identified in OneView by London Borough of Barking and Dagenham's Homes and Money hub and are receiving targeted support (this team is already using the OneView model to provide targeted support)

